### **Exploration of dose response relationship and the effects of induction dosing in terms of cardiovascular endpoints**

The method described in section 6.5 will be applied to assess dose response on cardiovascular endpoints over the whole duration of the trial.

It will be explored whether the early high induction dose regimen in 300 mg canakinumab arm has an impact on early (within 90 days of randomization) primary and secondary clinical cardiovascular events when compared to the placebo arm and to the 150 mg and 50 mg canakinumab arms, which have no early high induction dose regimen. For this purpose the primary endpoint and its components will be assessed over 90 days post-randomization. Similarly, the primary endpoint and its components will also be assessed at 6 months and 1 year, repeatedly.

#### **6.3.2 Key secondary efficacy variables**

The following hypotheses will be tested with respect to the key secondary variables for the canakinumab 300 mg dose versus placebo

- $H_{12}$ : The hazard rate of adjudication committee confirmed secondary composite CV endpoint in the canakinumab 300 mg dose group is greater than or equal to the hazard rate of the placebo group
- $H_{13}$ : The hazard rate of adjudication committee confirmed new onset of diabetes for pre-diabetic patients in the canakinumab 300 mg dose group is greater than or equal to the hazard rate of the placebo group

Each null hypothesis is tested against the one-sided alternative that the hazard rate is smaller for the canakinumab 300 mg dose group than in the placebo group. The corresponding hypotheses for the comparison of the canakinumab 150 mg dose versus placebo are  $H_{22}$  for the secondary composite CV endpoint and  $H_{23}$  for the new onset of diabetes endpoint. For the 50 mg dose they are  $H_{32}$  for the secondary composite CV endpoint and  $H_{33}$  for the new onset of diabetes endpoint.

[figure not shown]
All key secondary efficacy variables will be analyzed on the FAS and PPS1 with a log-rank test stratified by time since index MI and trial part. The hazard ratios will be estimated using a Cox regression model stratified by time since index MI and trial part.

Kaplan-Meier plots showing each treatment will be provided overall and by trial part as described in [section 6.4](#). The multiplicity adjustment used to protect the familywise type I

error rate is shown in [Figure 6-4](#) and showing the full details of testing the key secondary endpoints in [Figure 6-5](#). For each dose analyses of key secondary endpoints will be conducted even if the primary null hypothesis for the dose has not been rejected, but formally no rejection of the null hypotheses for the key secondary endpoints will be possible in that case.

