Sites are required to call the IVRS/IWRS at the prescreening and screening visit and at each visit to register their patient's status and if applicable, receive the medication numbers to

dispense treatment. Dispensing of medication should be the last assessment performed at each visit.

[figure not shown]
[figure not shown]
[figure not shown]

Table 6-1 Assessment schedule of pivotal phase

Visit	Pre-Screen	1	2	2.5	3	4	5	6	7	8	9	10	11	12,16, 20,24 ⁸	13,17, 21, 25 ⁸	14,18, 22,26 ⁸	15,19, 23,27 ⁸	End of Study (EOS)
Month		-1	0	0.5	1.5	3	6	9	12	15	18	21	24	27,39, 51,63...	30,42, 54, 66...	33,45, 57,69...	36,48, 60,72...	event driven
Obtain informed consent		X																
Prescreening Informed Consent	X																	
Height		X																
Inclusion/Exclusion		X																
Labs for entry criteria only:, HIV Screen, HBsAg and HCV antibody [For Japan only] [In Japan, HBc antibody and HBs antibody are additionally included]		X																
Hs-CRP	X ¹⁰	X ⁷	X	X	X	X	X	X	X		X		X		X		X	X
Determination of tuberculosis status ¹		X																
Demography																		
Demography		X																
History of CV Disease		X																
Medical History/Current Conditions		X																
Family History of CV disease			X															
Smoking & Alcohol History			X															
Treatment Assessments																		
Call IVRS/IWRS	X	X	X	X	X	X	X	X	X	X	X	X	X	X	X	X	X	X
Drug Administration			X	X		X	X	X	X	X	X	X	X	X	X	X	X	
Prior & Concomitant Antidiabetic & CVD Medications		X	X	X	X	X	X	X	X	X	X	X	X	X	X	X	X	X
Concomitant Medications ¹¹		X	X	X	X	X	X	X	X	X	X	X	X	X	X	X	X	X

[figure not shown]
[figure not shown]

Visit	Pre-Screen	1	2	2.5	3	4	5	6	7	8	9	10	11	12,16, 20,24 ⁸	13,17, 21, 25 ⁸	14,18, 22,26 ⁸	15,19, 23,27 ⁸	End of Study (EOS)	
Month		-1	0	0.5	1.5	3	6	9	12	15	18	21	24	27,39, 51,63...	30,42, 54, 66...	33,45, 57,69...	36,48, 60,72...	event driven	
Efficacy Assessments																			
Potential endpoint assessment				X	X	X	X	X	X	X	X	X	X	X	X	X	X	X	X
HbA1c & FPG (all patients) ²		X	X	X	X	X	X	X	X		X		X		X		X		X
Safety Assessments																			
Physical Exam			X						X				X					X	X
Vitals (includes BMI, weight, waist circumference)		X	X	X	X	X	X	X	X		X		X		X		X		X
ECG			X						X				X					X	X
Standard Hematology & Chemistry		X	X	X	X	X	X	X	X		X		X		X		X		X
Fasting Lipid Profile ³		X	X	X	X	X	X	X	X		X		X		X		X		X
Immunological (e.g. ANA) Screen			X																X ¹²
AE (prompting for infections)			X	X	X	X	X	X	X	X	X	X	X	X	X	X	X	X	X

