9.5.1 Secondary variables

Key secondary efficacy variables

The following key secondary variables will be used in the analyses:

- Time to the first occurrence of an adjudication committee confirmed composite cardiovascular endpoint consisting of the components of the primary endpoint and hospitalization for unstable angina requiring unplanned revascularization
- Time to adjudication committee confirmed new onset of type 2 diabetes among those with pre-diabetes at randomization

[figure not shown]
The following hypotheses will be tested with respect to the key secondary variables for the canakinumab 300 mg dose versus placebo

- H_{12} : The hazard rate of first adjudication committee confirmed secondary composite CV endpoint in the canakinumab 300 mg dose group is greater than or equal to the hazard rate of the placebo group
- H_{13} : The hazard rate of new onset of diabetes for pre-diabetic patients in the canakinumab 300 mg dose group is greater than or equal to the hazard rate of the placebo group

Each null hypothesis is tested against the one-sided alternative that the hazard rate is smaller for the canakinumab 300 mg dose group than in the placebo group. The corresponding hypotheses for the comparison of the canakinumab 150 mg dose versus placebo are H_{22} for the secondary composite CV endpoint and H_{23} for the new onset of diabetes endpoint; the corresponding hypotheses for the comparison of the canakinumab 50 mg dose versus placebo are H_{32} for the secondary composite CV endpoint and H_{33} for the new onset of diabetes endpoint.

All key secondary efficacy variables will be analyzed on the FAS with a log-rank test stratified by time since index MI and trial part. The hazard ratios will be estimated using a Cox regression model stratified by time since index MI and trial part. Kaplan-Meier type plots showing each treatment will be provided overall and separately by trial part. The multiplicity adjustment used to protect the familywise type I error rate is shown in [Figure 9-1](#). Based on this testing procedure, once the primary null hypothesis for a dose has been rejected the key secondary endpoints for that dose are tested using a weighted Bonferroni-Holm test ([Holm 1979](#)) at the available local significance level for the key secondary endpoints for that dose. The weighting of this Bonferroni-Holm procedure will be 90% for the key secondary CV composite and 10% for the key secondary new onset of diabetes endpoint.

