**Figure 6-5 Closed testing procedure with full details of testing of key secondary endpoints**

This figure as compared to [Figure 6-4](#) shows the full details of the Bonferroni-Holm procedure for the key secondary endpoints in a graphical form, but is otherwise identical in content.

Based on this testing procedure, once the primary null hypothesis for a dose has been rejected the key secondary endpoints for that dose are tested using a weighted Bonferroni-Holm test ([Holm 1979](#)) at the available local significance level for the key secondary endpoints for that dose. The weighting of this Bonferroni-Holm procedure will be 90% for the key secondary CV composite and 10% for the key secondary new onset of diabetes endpoint.

The secondary efficacy variable corresponding to new onset diabetes in patients with pre-diabetes at randomization will be the time from randomization to the first of repeated FPG  $\geq$  126 mg/dL or the first of repeated HbA1c  $\geq$  6.5% or start of new anti-diabetic concomitant medication(s) for glucose lowering purpose. All identified cases of new onset of diabetes will be confirmed by the adjudication committee.

Due to the discrete nature of the visits when new onset of type 2 diabetes can be determined, events identified at the same visit time point as defined in [section 2.3.6](#) for different patients will be considered as tied events and the exact method for handling ties will be used. This assumes that for each of these patients new onset of diabetes occurred at some time point since the previous visit, but that due to the impossibility of continuous monitoring of the patients the true order in which each of them progressed to diabetes is unknown ([Allison 1995](#),

pp. 127 to 137). For this variable patients without new onset of diabetes will be considered censored at the time of their last laboratory assessment. Patients not diagnosed at a regular visit or at the study completion visit will be assigned to one of the scheduled visits as per the algorithm in [section 2.3.6](#).

Subgroup analyses as specified in Table 2-3-1 will be conducted for the key secondary new onset of diabetes endpoint. These will include subgroup analyses by race, which could potentially influence HbA1c levels.

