### **Supportive and sensitivity analyses for key secondary endpoints**

To support the analysis for the new onset of diabetes endpoint, the criteria defining new onset will be presented, the diagnostic values causing diagnosis summarized and sensitivity analyses conducted based on each criterion alone.

The three pooled canakinumab doses will be compared to placebo on the key secondary endpoints. Additionally, comparisons between the canakinumab doses will also be reported using the pre-specified log-rank test with hazard ratios reported based on Cox regression.

Additionally, Kaplan-Meier plots will be provided separately for each of the followings:

- Time to adjudication committee confirmed new onset of type 2 diabetes among those with normoglycemic at randomization
- Time to adjudication committee confirmed new onset of type 2 diabetes among those with either pre-diabetes or normoglycemic at randomization
- Time to first pre-diabetes among those with normoglycemic at randomization.

The key secondary cardiovascular endpoint will also be analyzed adjusting for the same covariates used for the covariate adjusted analysis of the primary variable.

The key secondary endpoint new onset of diabetes will also be supported by analyses using data from the study's washout period. These analyses will be defined in a separate analysis

plan for the washout period and will be reported in a separate study report or addendum to the main study report.

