#### **7.4.8 Hypoglycemia**

As per the draft FDA requirements for the evaluation of prevention of diabetes, rates of hypoglycemia will be compared statistically between groups. Hypoglycemic events will be identified using the the SMQ Hypoglycaemia. Comparisons between treatment groups will be both done as time to first event analyses (including reporting the number of affected patients), as well as analyzing count data (number of patients with a certain number of hypoglycemic episodes – i.e. none, 1 episode, 2 episodes etc.) using negative binomial regression as described in [section 7.2](#). Baseline glucose and HbA1c values will be used as covariates in analyses.

Such reporting will be done for all hypoglycemic events as well as for events classified as severe by the investigator and events classified by the investigator as SAEs.

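### The alpha-controlled new-onset diabetes test is valid but leaves out baseline HbA1c and FPG, so it probably gives up power

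*SAP*

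**What the plan says.** SAP 6.3.2 has the key secondary variables "analyzed on the FAS and PPS1 with a log-rank test stratified by time since index MI and trial part". For estimation it says: "The hazard ratios will be estimated using a Cox regression model stratified by time since index MI and trial part". Protocol 9.5.1 agrees: "All key secondary efficacy variables will be analyzed on the FAS with a log-rank test stratified by time since index MI and trial part".

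The diabetes event is the earliest of three things: a repeated FPG of at least 126 mg/dL, "or the first of repeated HbA1c" of at least 6.5%, "or start of new anti-diabetic concomitant medication(s) for glucose lowering purpose". Protocol Table 6-1 schedules HbA1c and FPG for all patients at Visits 1 and 2. The same measures select the at-risk group. Protocol section 4 defines pre-diabetes as HbA1c 5.7-6.4% or FPG 100-125 mg/dL at either visit. SAP Table 2.3-1 also admits patients with a diabetic-range value at only one visit.

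On adjustment, the supportive part of SAP 6.3.2 says: "The key secondary cardiovascular endpoint will also be analyzed adjusting for the same covariates used for the covariate adjusted analysis of the primary variable". It has no matching sentence for diabetes. The covariate list it points to (SAP 6.3.1) contains glycemic status but neither an HbA1c nor an FPG value. For hypoglycemia, SAP 7.4.8 does adjust: "Baseline glucose and HbA1c values will be used as covariates in analyses".

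**The concern.** A patient who enters at HbA1c 6.4% is much closer to the event threshold than one at 5.7%. That distance is known before randomization and should predict the event. The two strata in use are a cardiovascular factor and a recruitment factor.

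Leaving a strong predictor out of a time-to-event comparison moves the marginal hazard ratio toward 1 relative to the conditional one, and it lowers power. Design does not make up for this: randomization is stratified only by time since MI, and sites report glycemic status at Visit 3, after randomization (Protocol 5.3). Glycemic status in the covariate list cannot help either, because it is constant among pre-diabetic patients.

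The endpoint has little power to spare. It starts with 10% of the level passed to a dose's key secondary hypotheses. The 1,400-event target was set on MACE alone, and Protocol 9.7 says the key secondary power calculations were not updated after Amendment 6.

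**Working it through.** **1. The plan's own figures.** The documents state no power, rate or event count for new-onset diabetes, so only the shared testing procedure can be checked.
- Weighted Dunnett levels (correlation 0.5, weights 0.2/0.4/0.4) recompute to 0.5498%/1.0996%/1.0996%, against the stated 0.5501%/1.1001%/1.1001%.
- Power for at least one dose with a 20% reduction in all doses recomputes to 94.5%, against 93.6% in Protocol Table 9-1.
- The 20/20/0 row gives 87.7% against 87.5%. The 17.5% row gives 86.0% against 83.7%, a looser match.

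**2. Level available to the diabetes test at the final analysis (one-sided).**
- 150 or 50 mg: at most 0.98% × 10% = 0.098%, before the CV composite for that dose is rejected or alpha arrives from another dose.
- 300 mg: 45% and 25% go to the other doses, leaving 30%. If all of that goes to the key secondaries, 0.49% × 30% × 10% = 0.0147%.
- If the CV composite is rejected, the Holm step releases its 90%. The level for 150 or 50 mg then rises to at most 0.98% from its own allocation.

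**3. Patients.** Protocol section 4 expects 35% pre-diabetic, and Protocol 5.2 gives 3,333 placebo and 2,253 on 150 mg. So 0.35 × 3,333 ≈ 1,167 and 0.35 × 2,253 ≈ 789.

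**4. Assumptions (none is in the documents).** Conditional HR 0.80 or 0.70; placebo incidence 12% or 25% over about 3.7 years; correlation of baseline HbA1c and FPG 0.3. Prognostic strength is the log HR per SD of HbA1c/FPG, set at 0.4/0.3, 0.7/0.5 or 1.0/0.6. The SD of the log-hazard is √(a² + b² + 2 × 0.3ab) = 0.57, 0.97 and 1.31.

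**5. Simulated power (%), unadjusted log-rank → Cox adjusted for both values, 2,500 trials per row.**

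| HR | Placebo incidence | Prognosis | At 0.98% | At 0.098% |
|---|---|---|---|---|
| 0.80 | 12% | 0.4/0.3 | 22.8 → 23.3 | 5.4 → 6.1 |
| 0.80 | 12% | 0.7/0.5 | 18.4 → 22.3 | 5.2 → 6.0 |
| 0.80 | 12% | 1.0/0.6 | 16.7 → 22.1 | 3.5 → 5.3 |
| 0.70 | 12% | 0.4/0.3 | 53.3 → 54.2 | 24.0 → 24.3 |
| 0.70 | 12% | 0.7/0.5 | 47.3 → 54.2 | 19.3 → 22.6 |
| 0.70 | 12% | 1.0/0.6 | 40.9 → 53.8 | 16.2 → 25.0 |
| 0.80 | 25% | 0.4/0.3 | 44.4 → 48.5 | 18.3 → 20.0 |
| 0.80 | 25% | 0.7/0.5 | 39.0 → 50.3 | 14.3 → 22.1 |
| 0.80 | 25% | 1.0/0.6 | 31.6 → 50.2 | 10.5 → 21.7 |
| 0.70 | 25% | 0.4/0.3 | 86.6 → 90.3 | 60.1 → 66.1 |
| 0.70 | 25% | 0.7/0.5 | 79.3 → 89.2 | 51.8 → 69.0 |
| 0.70 | 25% | 1.0/0.6 | 68.8 → 89.8 | 39.3 → 68.2 |

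The Monte Carlo standard error of one entry near 50% is √(0.25/2,500) = 1 point, so the smallest gains are not distinguishable from zero. As a ratio of squared mean Z, adjustment is worth 3% to 62% more events. With no prognostic value the two tests agree within 1 point. Under the null, rejection at nominal 2.45% was 2.5% unadjusted and 2.0% adjusted (6,000 runs), so adjustment showed no inflation.

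**6. Second simulation.** This used one normal baseline covariate with log-hazard SD 1.0 and 2.5 to 5 years of follow-up. Power is Φ(mean Z − z), with z = 2.334 at 0.98% and 3.096 at 0.098%.

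| HR | Events | Mean Z | At 0.98% | At 0.098% |
|---|---|---|---|---|
| 0.70 | 13% | 2.46 → 2.65 | 55.0 → 62.4 | 26.2 → 32.8 |
| 0.75 | 13% | 2.04 → 2.24 | 38.4 → 46.3 | 14.5 → 19.6 |
| 0.70 | 22% | 3.08 → 3.51 | 77.2 → 88.0 | 49.4 → 66.0 |
| 0.75 | 23% | 2.61 → 2.94 | 60.9 → 72.8 | 31.3 → 43.8 |

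The direction is the same, and so is the dependence on event count.

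**The case against.** The strongest reply is that nothing here is wrong. The log-rank test uses the randomization stratum and trial part, and it holds its level. SAP 6.3.1 values it because it needs no proportional-hazards assumption, whereas a Cox test relies on the form of the covariates. On this view, an unadjusted test is a legitimate preference. That stands as a defence of validity. It does not explain why a predictor already collected is left out, and the documents give no reason.

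The gain is also hypothetical, and that stands. If HbA1c alone carried a log-hazard SD of 1.0 and were uniform over 5.7-6.4% (SD 0.7/√12 = 0.20), the hazard would differ exp(0.7/0.20) ≈ 32-fold across the window. No document supports or refutes that. The simulated adjusted model was correctly specified and ran in continuous time. The plan has visit-based ties, four strata and a drug-start route.

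A reader might also infer more than the documents support:
- **That no adjusted diabetes analysis is planned.** None appears in the legible text, but parts of SAP 6.3 are redacted and SAP section 1 defers supportive detail to a fuller plan.
- **That the plan ignores baseline glycemia.** It uses it to define the population; only the test and its hazard ratio omit it.
- **That chance imbalance cannot be addressed.** Protocol 9.2 allows supplemental analyses if imbalances appear.
- **That the endpoint only ever gets 10%.** The Holm step can release the rest.
- **That the hypoglycemia analysis proves inconsistency.** It is a safety analysis without multiplicity control and is not limited to one glycemic group, so the comparison is only suggestive.

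**Conclusion.** The point holds as a matter of efficiency. The confirmatory diabetes test leaves out two baseline measures that are already collected and that sit on the same scales as two of the three event criteria. If they are prognostic, adjustment gains power at no cost in type I error.

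The size cannot be taken from the documents. Under the stated assumptions the gain runs from under 1 point (weak prognosis, 12% placebo incidence) to roughly 10-20 points or more (moderate to strong prognosis, 22-25% events). The largest gain was 28.9 points, at the 0.098% level with HR 0.70 and the strongest prognosis. Few events or weak prognosis make the matter minor.

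It would be wrong to read this as bias. The unadjusted hazard ratio lies nearer 1 partly because marginal and conditional hazard ratios are different quantities, and the current test controls its error rate.

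**What to change.** Before unblinding, amend SAP 6.3.2 and Protocol 9.5.1 so that H13, H23 and H33 are tested with the treatment test from a Cox model:
- stratified by time since index MI and trial part, with ties=exact;
- with baseline HbA1c and baseline FPG as continuous covariates, baseline being as in SAP 2.3.2 (last available value up to randomization; averaging is specified there only for hsCRP);
- with the test statistic named, for example the score test.

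State that the hazard ratio is conditional on baseline glycemia, and keep the current stratified log-rank test as a sensitivity analysis. The graphical procedure does not change, because the key secondary hypotheses are tested at weighted Bonferroni-Holm levels.

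No new data are needed. The costs are a conditional estimand, reliance on the covariate form, and a written protocol amendment with the approvals in Protocol 11.1. The SAP also needs a short rule for missing baseline values, which should be few because Protocol 6.5.4 requires missing screening results to be repeated before randomization. It needs another for the patients in whom SAP 6.3.2 regards HbA1c as unreliable.

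If reliance on covariate form is the worry, a log-rank test also stratified by tertiles of both values recovers part of the gain: 46.5% at the 0.98% level with HR 0.80, 25% incidence and prognosis 0.7/0.5, between 39.0% unadjusted and 50.3% with the Cox model.

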**Figure 6-5 Closed testing procedure with full details of testing of key secondary endpoints**

This figure as compared to [Figure 6-4](#) shows the full details of the Bonferroni-Holm procedure for the key secondary endpoints in a graphical form, but is otherwise identical in content.

Based on this testing procedure, once the primary null hypothesis for a dose has been rejected the key secondary endpoints for that dose are tested using a weighted Bonferroni-Holm test ([Holm 1979](#)) at the available local significance level for the key secondary endpoints for that dose. The weighting of this Bonferroni-Holm procedure will be 90% for the key secondary CV composite and 10% for the key secondary new onset of diabetes endpoint.

The secondary efficacy variable corresponding to new onset diabetes in patients with pre-diabetes at randomization will be the time from randomization to the first of repeated FPG  $\geq$  126 mg/dL or the first of repeated HbA1c  $\geq$  6.5% or start of new anti-diabetic concomitant medication(s) for glucose lowering purpose. All identified cases of new onset of diabetes will be confirmed by the adjudication committee.

Due to the discrete nature of the visits when new onset of type 2 diabetes can be determined, events identified at the same visit time point as defined in [section 2.3.6](#) for different patients will be considered as tied events and the exact method for handling ties will be used. This assumes that for each of these patients new onset of diabetes occurred at some time point since the previous visit, but that due to the impossibility of continuous monitoring of the patients the true order in which each of them progressed to diabetes is unknown ([Allison 1995](#),

pp. 127 to 137). For this variable patients without new onset of diabetes will be considered censored at the time of their last laboratory assessment. Patients not diagnosed at a regular visit or at the study completion visit will be assigned to one of the scheduled visits as per the algorithm in [section 2.3.6](#).

Subgroup analyses as specified in Table 2-3-1 will be conducted for the key secondary new onset of diabetes endpoint. These will include subgroup analyses by race, which could potentially influence HbA1c levels.

Given some patients may have medical conditions that elevate their HbA1c levels that are unrelated to diabetes (e.g. patients with hemoglobinopathies such as sickle cell disease, while several other conditions causing interference such as e.g. uremia, liver disease, alcoholism and drug (opiate) use are excluded from this protocol), a second set of new onset diabetes criteria will be defined. This second set of criteria will determine new onset diabetes for these patients based on having either (2 consecutive HbA1c  $\geq 6.5$  % and 2 consecutive FPG values  $\geq 126$  mg/dL from the same visits as HbA1c) or (HbA1c  $\geq 6.5$  % at one visit reported and FPG  $\geq 126$  mg/dL reported at same visit and FPG  $\geq 126$  confirmed at the consecutive visit) or 2 consecutive FPG values  $\geq 126$  mg/dL. The identification of these patients will be done in a blinded fashion by a medical monitor using medical history data and other baseline data. All patients deemed not to have any of these medical conditions will be assessed for new onset diabetes as described in the first set of criteria (see paragraph above). New onset of diabetes data will be reported overall and separately for these patients in whom diagnoses based on HbA1c levels is not appropriate (defined as “FPG  $\geq 126$  mg/dl at 2 occasions” or “Confirmed prescription and use of Diabetes Drug” based on the New Onset Diabetes (Adjudication) CRF page) The analysis described above will also be performed using this alternative new onset diabetes definition.

